Cover Page

Official Title: Postoperative Myofunctional Therapy Enhances Surgical Outcomes in Patients with Obstructive Sleep Apnea: A Prospective Comparative Study

NCT Number: NCT ID not yet assigned

Document Date: January 7, 2020 (Version 2.0)

Research Protocol

Part 1: Core Research Content

1. Project Summary

This study aims to prospectively compare surgical outcomes in patients with obstructive sleep apnea (OSA) who receive postoperative myofunctional therapy (OP+MFT) versus those who undergo surgery alone (OP). Obstructive sleep apnea (OSA) is a common disorder characterized by recurrent upper airway collapse. While surgical interventions are a common treatment, they yield variable success rates. Myofunctional therapy (MFT), which utilizes targeted oropharyngeal exercises, has emerged as a promising adjunctive treatment to improve these outcomes. This study will enroll adults with moderate-to-severe OSA. Following surgery, patients will be allocated to either the OP+MFT group, which will begin a 12-week MFT program, or the OP group. Polysomnography (PSG) will be performed at baseline and at 3 and 12 months post-surgery to assess efficacy. It is expected that the OP+MFT group will show significantly greater improvements in key sleep parameters, including the Apnea-Hypopnea Index (AHI), lowest oxygen saturation (LSaO₂), and snore index, compared to the OP group. The findings will provide evidence to support the integration of MFT into routine postoperative care for OSA patients.

2. General Information

- **Protocol Title:** Postoperative Myofunctional Therapy Enhances Surgical Outcomes in Patients with Obstructive Sleep Apnea: A Prospective Comparative Study.
- **Protocol Identifying Number:** TMUJIRB No.201912067.
- **Sponsor/Funder:** Taipei Medical University Shuang Ho Hospital Young Scholar Research Grant W114YSR-03 and Taipei Medical University Newly Recruited Faculty Research Grant, Project No. TMU113-AE1-B04
- **Investigator(s) and Site:**
 - **Principal Investigator:** [name] (Corresponding Author).
 - **Co-Investigators:** [name], [name], [name], [name], [name]
 - **Research Site:** Taipei Medical University-Shuang Ho Hospital.
- **Involved Clinical and/or Technical Departments:**
 - Department of Otolaryngology, Shuang Ho Hospital.
 - Sleep Center, Shuang Ho Hospital.

- Speech-Language Pathologist services.

3. Rationale & Background Information

Obstructive Sleep Apnea (OSA) is a prevalent condition associated with significant morbidity, including hypertension and cardiovascular disease. Continuous positive airway pressure (CPAP) is the first-line treatment, but adherence is notoriously poor, with long-term compliance as low as 10-20%. For patients intolerant to CPAP, surgical options are offered, yet their long-term success rates average only 30%.

Myofunctional therapy (MFT) addresses the functional dimension of OSA by strengthening oropharyngeal muscles to increase airway stability. A meta-analysis has already demonstrated that MFT alone can reduce the AHI by 50% in adults. The rationale for this study is that surgery primarily addresses static anatomical obstructions, while MFT targets the functional deficit of poor neuromuscular tone that surgery alone cannot correct. We hypothesize that a combined, synergistic approach-where surgery provides anatomical relief and MFT enhances dynamic airway stability-will lead to superior treatment outcomes compared to surgery alone.

4. Study Goals and Objectives

- **Goal:** To determine if adding a structured postoperative MFT program to sleep surgery improves treatment outcomes for patients with moderate-to-severe OSA compared to surgery alone.
- **Primary Objective:**
 - To compare the reduction in AHI at 3 and 12 months post-surgery between the OP+MFT and OP-only groups, with success defined as >50% AHI reduction and a final AHI <20 events/hour.
- **Secondary Objectives:**
 - To compare the change in lowest oxygen saturation (LSaO₂) between the groups at 3 and 12 months.
 - To compare the change in the snore index between the groups at 3 and 12 months.

5. Study Design

This is a prospective, single-surgeon, non-randomized controlled study conducted at a single medical center.

- **Research Population:** Adults aged 20-65 with moderate-to-severe OSA (AHI ≥ 15 events/hour) confirmed by PSG.
- **Inclusion Criteria:**
 - Age 20-65 years.
 - Moderate-to-severe OSA (AHI ≥ 15 events/hour)
 - Friedman palate position grade I-II and tonsil size grade III-IV.
 - Patients who refuse or are unable to tolerate CPAP.
- **Exclusion Criteria:**
 - Central or mixed sleep apnea.
 - BMI $> 27 \text{ kg/m}^2$.
 - Severe cardiopulmonary disease or psychiatric illness.
 - Pregnancy or cancer.
 - Significant weight gain during the follow-up period.
- **Study Duration:** The project was conducted between January 2020 and January 2024. Each participant's follow-up duration is 12 months.

6. Methodology

- **Interventions:**
 - **Surgery:** All patients will undergo surgery performed by the same surgeon, including uvulopalatopharyngoplasty (UPPP) and adjunctive nasal turbinate reduction surgery.
 - **Grouping:** After surgery, enrolled patients will be divided into two groups based on personal willingness: Group A (OP+MFT) or Group B (OP- only).
 - **Myofunctional Therapy (MFT):** Group A patients will begin a 12-week MFT program starting at the third postoperative week. The program includes:
 - Initial Instruction: Two face-to-face training sessions with a speech-language pathologist in the first week.
 - Home Practice: Twice-daily sessions of 15 minutes each, guided by instructional videos.
 - Exercises: Tongue elevation and protrusion drills, soft palate elevation, pharyngeal wall contractions, and nasal breathing retraining.
 - Supervision: Biweekly review sessions with the therapist to ensure correct performance and adherence.
- **Outcome Measures & Procedures:**

- All participants will undergo overnight polysomnography (PSG) at the sleep center at baseline (pre-surgery), and at 3 and 12 months post-surgery.
- Objective data on AHI, LSaO₂, and snore index will be collected.
- **Study Flow Diagram:** [Eligible OSA Patients] -> [Informed Consent] -> [Baseline PSG] -> [Undergo Surgery (UPPP)] -> [Post-op Group Allocation] ---> [Group A: OP+MFT] -> [12-Week MFT Program] ---> [3-Month PSG Follow-up] -> [12-Month PSG Follow-up] -> [Data Analysis] | +--> [Group B: OP-only] -> [Routine Follow-up] -----+

7. Safety Considerations

Participant safety is paramount. MFT is a non-invasive therapy with minimal risk.

- All surgical procedures will be performed by an experienced surgeon, and standard postoperative care protocols will be followed to manage potential complications such as pain or bleeding.
- The intensity of MFT exercises will be introduced gradually to prevent muscle strain.
- During all follow-up visits, researchers will actively monitor and record any adverse events related to either the surgery or the MFT. All adverse events will be reported to the Institutional Review Board (IRB) in accordance with regulations.

8. Data Management and Statistical Analysis

- **Data Management:** All research data will be de-identified and coded. The data will be entered into a password-protected electronic database accessible only to the research team.
- **Statistical Analysis:**
 - Continuous variables will be compared using paired or unpaired t-tests.
 - Categorical outcomes will be compared using the chi-square test.
 - A p-value of <0.05 will be considered statistically significant.

9. Quality Assurance

To ensure the quality and consistency of the study:

- All surgeries will be performed by a single surgeon to standardize the surgical technique.
- All MFT instruction and supervision will be conducted by the same speech-language pathologist to ensure consistency in the training protocol.

- All PSG data will be scored according to the standardized guidelines of the American Academy of Sleep Medicine.
- The study will be conducted in strict adherence to the IRB-approved protocol and Good Clinical Practice (GCP) guidelines.

10. Expected Outcomes of the Study

This study is expected to demonstrate that the addition of postoperative MFT significantly enhances the efficacy of surgical treatment for OSA. The findings will provide strong evidence for a multimodal treatment strategy, potentially influencing future clinical guidelines for OSA management. This research will advance the understanding of OSA pathophysiology by highlighting the importance of addressing both anatomical and neuromuscular functional deficits.

11. Dissemination of Results and Publication Policy

The results of the study will be submitted for publication in a peer-reviewed international medical journal. Authorship will be determined based on the contributions of each member of the research team, as detailed in the "Authors' contributions" section of the manuscript.

12. Duration of the Project

The total duration of the project is four years, from January 2020 to January 2024.

- Year 1: Patient recruitment, surgical interventions, and early postoperative follow-up.
- Years 2-3: Continued recruitment and completion of all 3-month and 12-month follow-up assessments.
- Year 4: Data compilation, statistical analysis, and manuscript preparation and submission.

13. Problems Anticipated

- **Problem:** The modest sample size may limit statistical power.
 - **Solution:** Future research could be designed as a larger, multi-center trial.
- **Problem:** The 12-month follow-up period does not capture long-term recurrence.
 - **Solution:** Future studies should extend the follow-up period to three to five years.
- **Problem:** Adherence to MFT was based on self-report, which could introduce bias.

- **Solution:** Future protocols could incorporate digital tools, such as smartphone apps, for more objective adherence monitoring.

14. Project Management

- **Conceptualization & Supervision:** [name], [name]
- **Data Curation:** [name], [name]
- **Formal Analysis & Methodology:** [name], [name], [name]
- **Investigation:** [name]
- **Writing & Editing:** All authors contributed.

15. Ethics

The study protocol has received ethical approval from the Taipei Medical University Joint Institutional Review Board (TMUJIRB No.201912067). All participants will provide written informed consent before enrollment. Participants will be informed of the study's purpose, procedures, potential risks, and benefits, and will be notified that they can withdraw from the study at any time without penalty.

16. Informed Consent Forms

Copies of the IRB-approved Informed Consent Forms (in both English and Traditional Chinese) will be appended to this protocol. The forms will ensure that participants have all the necessary information to make a voluntary and informed decision about their participation.

Part 2: Administrative and Supporting Documents

1. Budget

This research is funded by the Taipei Medical University Shuang Ho Hospital Young Scholar Research Grant W114YSR-03 and Taipei Medical University Newly Recruited Faculty Research Grant, Project No. TMU113-AE1-B04

2. Other Support for the Project

None.

3. Collaboration with other scientists or research institutions

This project involves collaboration between researchers at Taipei Medical University, Shuang Ho Hospital, National Yang Ming Chiao Tung University, and National Tsing Hua University.

4. Curriculum Vitae of Investigators

The CVs of the Principal Investigator and co-investigators are attached.

5. Financing and Insurance

Participants in this study are covered by the clinical trial liability insurance of the conducting institution, Taipei Medical University-Shuang Ho Hospital

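### Neither visit and neither form of the AHI outcome is designated primary, so the error rate of the main claim is unspecified

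*Combined protocol and SAP*

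**What the plan says.** The primary objective in Section 4 of the combined protocol and SAP is one sentence: "To compare the reduction in AHI at 3 and 12 months post-surgery between the OP+MFT and OP-only groups, with success defined as", followed by the criterion. The full criterion reads "with success defined as >50% AHI reduction and a final AHI <20 events/hour". The word for the last AHI value is not tied to a visit. The two secondary objectives, on LSaO₂ and snore index, are also set at both visits.

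The statistical analysis in Section 8 has three lines. The threshold, common to all tests, is the last of them: "A p-value of <0.05 will be considered statistically significant". Of the two lines on methods, the first covers measures such as AHI reduction: "Continuous variables will be compared using paired or unpaired t-tests". The second assigns a chi-square test to categorical outcomes, which would include success.

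Neither section assigns a test to the primary objective, ranks the visits or the two forms of the outcome, or gives a test order or a multiplicity adjustment. Neither says whether one significant result or all of them are needed. No other section fills the gap. Section 8 reads as complete, so this is not text lost to redaction or conversion.

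**The concern.** A significance level is the error rate of a claim only when the plan says which result makes the claim. Here several rules fit the text: either AHI comparison, both of them, success at one or both visits, or any of these. A significant result at 3 months alone, or on success alone, could be reported as meeting the primary objective, and the rule could be settled after the results are known.

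This matters because Section 10 expects strong evidence that might shape clinical guidelines. A reader of the final report would take p<0.05 as a 5% error rate, and the plan does not support that.

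**Working it through.** **Inputs from the documents.** Threshold 0.05 for each test (Section 8); two visits and two outcome forms (Section 4); the same patients measured at both visits (Section 6), so the tests are correlated. Sidedness is not stated, and I take the tests as two-sided.

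**Inputs assumed, because the documents give none.** Groups of 20/20, 30/30, 50/50 or 20/40; between-visit residual correlation 0.3, 0.5, 0.7 or 0.9; log-normal baseline AHI of at least 15 with median about 40; median residual AHI 40% or 60% of baseline with log-SD 0.7, giving success in about 52% or 31%; comparable groups; no true effect. This makes 4 × 4 × 2 = 32 settings, with 20,000 simulated trials each.

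**Step 1: the plan's own figure.** For k independent tests, the chance of at least one false positive is 1 − (1 − 0.05)^k.
- k = 1: 1 − 0.95 = 5.00%, the stated level.
- k = 2: 1 − 0.95² = 9.75%.
- k = 4: 1 − 0.95⁴ = 18.55%.

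The stated 5% is reproduced only if one test carries the claim.

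**Step 2: two correlated visits.** With bivariate normal test statistics, P(either) = 1 − P(|Z₁| < 1.96 and |Z₂| < 1.96), and P(both) = 0.05 + 0.05 − P(either).

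| Correlation | Either visit | Both visits |
|---|---|---|
| 0.3 | 9.51% | 10 − 9.51 = 0.49% |
| 0.5 | 9.07% | 10 − 9.07 = 0.93% |
| 0.7 | 8.35% | 10 − 8.35 = 1.65% |
| 0.9 | 7.04% | 10 − 7.04 = 2.96% |

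If the effect were real at one visit only, the both-visits rule could approach 5% but not pass it, because the test at the other visit must still reject.

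**Step 3: simulation with skewed AHI.** Unpaired t-test on AHI reduction and chi-square on success at each visit; errors in either direction are counted.

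| What counts as positive | Uncorrected chi-square | Continuity-corrected |
|---|---|---|
| Either AHI test | 6.0-9.2% (no chi-square) | same |
| Both AHI tests | 0.4-3.0% (no chi-square) | same |
| Success at either visit | 6.5-10.7% | 2.8-6.7% |
| Success at 12 months only | 4.0-5.7% | 1.6-3.5% |
| Any of the four | 12.1-18.0% | 8.8-14.5% |

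Counting only errors that favour MFT, the either-AHI rule gives 2.6-4.5%, against 2.5% for a single test.

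**Step 4: after the fix.** In a fixed order, no later test is reached unless the first is significant. With no true effect, the overall rate is therefore that of the first test. For 12-month AHI adjusted for baseline this was 4.2-5.0% on the raw scale and 4.7-5.3% on the log scale.

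**Step 5: why adjust for baseline.** In Section 6, "enrolled patients will be divided into two groups based on personal willingness". In a separate run with one visit and 20, 30 or 50 per group, I assumed that this left median baseline AHI at 50 in one group and 40 in the other. A single unadjusted t-test on change then gave 5.6-17.6% false positives, and the adjusted test 4.2-5.2%.

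**The case against.** The grammar of the primary objective favours a narrower reading. What is compared is the AHI reduction, and success is only a subordinate definition. The key parameters in Section 1 and the data listed in Section 6 are AHI, LSaO₂ and snore index, without success. This stands: two AHI tests is the more natural reading, so 6-9% is the figure to lead with. The 12-18% needs the wider reading and uncorrected chi-square tests.

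It is also fair that no section says any one positive test suffices, and that co-primary visits are legitimate when both are required. A reader might infer that the plan is shown to run above 5%. The documents do not support that, because some rules that fit the text stay at or below 5%. What stands is that no rule is written.

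Three other inferences should be resisted.
- That no outcome is named. Both forms are named; neither is designated primary.
- That a within-group paired test might decide the primary question. Section 4 states a between-group comparison, so the unpaired test follows, and the Section 8 line is a general list of methods.
- That the outcomes had already been seen. Past-tense wording in Sections 5 and 13 makes this plausible but does not prove it.

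Finally, selection from patient-chosen groups may be the larger threat. That is a separate problem, and it does not remove this one.

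**Conclusion.** The point holds as one of specification. The plan joins two unranked visits and two unranked outcome forms in one primary objective and tests each at 0.05, so its main claim has no defined error rate. The percentages are illustrations that rest on the assumed group sizes, AHI distribution and correlation, and on comparable groups; they are not bounds. The excess over 5% under an either-visit rule is moderate, and smaller still if only errors in favour of MFT are counted. The plan should be corrected, but the gap does not by itself invalidate the study.

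**What to change.** In Sections 4 and 8, name one primary test: the between-group difference in 12-month AHI, adjusted for baseline AHI, at two-sided 0.05. Twelve months is supported by the plan itself: Section 5 says of each participant that "follow-up duration is 12 months", and it fits the reference to a final AHI.

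Then test the remaining primary-objective comparisons in a stated fixed order, each at 0.05 and only if the one before it is significant. One example is success at 12 months, AHI at 3 months, then success at 3 months. A Holm procedure over all four should not be offered as an alternative, because it would again let a 3-month-only or success-only result carry the claim.

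Report LSaO₂ and snore index as secondary, with confidence intervals and no confirmatory claim. State that these steps deal with multiplicity and with measured imbalance in baseline AHI only, not with other selection bias from patient-chosen groups. If outcome data have already been seen, label the choice post hoc.

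The cost is text only, with no new patients or measurements. The sponsor gives up the option of resting the primary claim on 3 months alone or on success alone. If data have been seen, the sponsor also cannot present the result as a pre-specified confirmation.

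### The exclusion for weight gain during follow-up removes patients after surgery and grouping, on an undefined event, and can bias the group comparison in either direction

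*Combined protocol and SAP*

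**What the plan says.** Section 5 (Study Design, Exclusion Criteria) ends its list with "Significant weight gain during the follow-up period". The same section states that "Each participant's follow-up duration is 12 months".

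Section 6 (Methodology, Grouping) says that "After surgery, enrolled patients will be divided into two groups based on personal willingness". The flow diagram in that section runs from consent to baseline PSG, surgery, group allocation and only then follow-up.

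The outcome data listed in section 6 are AHI, LSaO₂ and snore index; follow-up weight is not listed. The only other weight criterion is the BMI limit of 27 kg/m² in section 5, and it is not linked to weight gain.

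Section 8 (Data Management and Statistical Analysis) provides for paired or unpaired t-tests and a 0.05 significance level, and states "Categorical outcomes will be compared using the chi-square test". It defines no analysis set, no handling of patients excluded after treatment, no missing-data rule and no sensitivity analysis.

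**The concern.** An eligibility criterion should depend on facts known before treatment. This one depends on an event in the 12 months after surgery, so it selects on something that follows treatment and may be related to outcome.

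Because *significant* is undefined and no blinding is described, whether a patient counts as a weight gainer could be decided with the group and the 3-month AHI already known. Valid 3-month data could be discarded along with the patient.

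The groups are already self-selected and the tests are unadjusted, so this adds a second selection to a comparison that randomisation does not protect. Success within each group can also be inflated if those removed are mostly failures. Finally, the result would describe patients who stay weight-stable, whereas the goal in section 4 is to learn whether MFT "improves treatment outcomes for patients with moderate-to-severe OSA compared to surgery alone".

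**Working it through.** **Order of events.** Consent, baseline PSG, surgery and grouping all precede follow-up, and the criterion refers to follow-up. It can therefore only act on patients already treated and grouped.

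**No figure to reproduce.** The documents give no sample size, exclusion rate or dropout rate. What follows shows only how such a rule can behave.

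**Inputs.** True success p = 0.30 is the figure section 3 gives for the long-term success of surgery. Assumed: the share removed in each group, r; the share of those removed who are failures, f; and 30 patients per group, since section 13 says only that the sample is modest.

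**Formula.** Observed success after removal = (p − r(1 − f)) / (1 − r).

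**No true effect, 20% removed from one group and 5% from the other:**

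| f | 20% removed | 5% removed | Difference |
|---|---|---|---|
| 1.00 | 0.30/0.80 = 37.5% | 0.30/0.95 = 31.6% | 5.9 points |
| 0.90 | 0.28/0.80 = 35.0% | 0.295/0.95 = 31.1% | 3.9 points |
| 0.85 | 0.27/0.80 = 33.75% | 0.2925/0.95 = 30.8% | 3.0 points |
| 0.70 | 0.24/0.80 = 30.0% | 0.285/0.95 = 30.0% | 0 |

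The sign depends on which group loses more patients. At f = 0.90, OP+MFT minus OP is +3.9 points if OP+MFT loses 20% and OP 5%, and −3.9 points if the shares are reversed.

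**In counts.** With 9 successes out of 30 in each group, removing 4 failures from one and 1 from the other gives 9/26 = 34.6% versus 9/29 = 31.0%, a gap of 3.6 points.

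**With a true effect.** Suppose true success is 50% with OP+MFT and 30% with OP (+20 points), and f = 0.90.
- 5% removed from OP+MFT and 20% from OP: 0.495/0.95 − 0.28/0.80 = 52.1% − 35.0% = +17.1 points.
- 20% removed from OP+MFT and 5% from OP: 0.48/0.80 − 0.295/0.95 = 60.0% − 31.1% = +28.9 points.

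**Selective use of an undefined threshold.** Suppose 15% gain weight in each group and 10% of the gainers are successes. If only the failing gainers are removed from one group and nobody from the other, that group shows 0.30/(1 − 0.15 × 0.90) = 0.30/0.865 = 34.7% against 30.0%, a gap of 4.7 points with no true effect.

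**Equal removal.** Removing 20% from both groups, all failures and with no true effect, gives no between-group difference but raises success within each group from 30% to 37.5%.

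**False-positive rate** (simulation, 30 per group, 30% success in both, uncorrected chi-square at 0.05):

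| Removed | f | Rate |
|---|---|---|
| none | – | 4.8% |
| 10% and 10% | 1.00 | 5.1% |
| 10% and 5% | 1.00 | about 5.3% |
| 20% and 5% | 0.85 | about 5.8% |
| 20% and 5% | 1.00 | 7.8% |
| 20% and 0% | 1.00 | 9.3% |

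**The case against.** The protocol never says that anyone was removed, or whether exclusion means leaving the analysis, stopping follow-up or losing only the later PSGs. That is true. But removal is the ordinary meaning of an exclusion criterion, and the silence is part of the fault.

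The larger figures need strong assumptions. A false-positive rate near 8% requires a fourfold imbalance in removal and every removed patient to be a failure; milder cases stay below 6%. The 30% is a general long-term average for surgery, not a 3- or 12-month rate in this selected population. The primary objective also compares AHI reduction itself, which the success-rate illustration does not cover. All of this stands as a limit on size. It does not touch the mechanism.

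There is a reasonable motive for the rule: holding weight constant may help to isolate the effect on the airway. A weight-stable question is legitimate if it is defined in advance and reported beside an analysis of all patients. Weight change after grouping is not a baseline confounder, however, so it should not decide who enters the main comparison. The population is also already narrowed by BMI, anatomy and CPAP refusal or intolerance, so the loss of generality is the lesser part of the problem.

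Lastly, self-selected grouping with unadjusted tests is a separate source of bias that this correction leaves in place. That is so, and it is no reason to add another.

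**Conclusion.** The concern holds and should be corrected before the results are relied on. The plan contains a stated rule that takes treated and grouped patients out of the comparison on an undefined later event, and nothing else in the document offsets it.

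That the rule can bias the result is certain; that it has done so, by how much and in which direction cannot be known from the documents. With no true effect, the illustrations run from zero to about 6 points of spurious difference in success, with either sign. Around a true 20 points they run from 2.9 points too low to 8.9 too high. Of the inputs, only the 30% comes from the protocol; group size, removal shares, failure rate among those removed and the 50% alternative are assumptions. The between-group bias disappears when those removed fail at the same rate as everyone else and, if MFT has no effect, when removal and failure rates among those removed are equal across groups.

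**What to change.** 1. Delete the weight-gain line from the exclusion criteria in section 5.
2. State in section 8 that the primary analysis includes every operated and grouped patient with PSG data, whatever their later weight. Restore any patient already removed whose PSG data exist, including those with only a 3-month recording.
3. Report by group how many patients were removed or met the criterion, and how many therefore have no 12-month PSG.
4. Keep the exclusion of weight gainers only as a labelled sensitivity analysis, with a numeric cut-off fixed before data review and based on weights recorded at the PSG visits where available. If the data have already been reviewed, label the cut-off as post hoc.

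The cost is one line of the protocol, a sentence in section 8 and a count by group. AHI results may be slightly noisier or less favourable. Section 5 describes the project in the past tense, as running from January 2020 to January 2024. If collection has ended, follow-up weights may be incomplete, which limits the sensitivity analysis. Patients withdrawn before their 12-month PSG cannot be recovered at that time point, so selection there may remain and should be stated as a limitation. The primary analysis otherwise needs only PSG data that already exist.

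### Group choice comes after surgery, so early recovery can enter the comparison, and no planned measure or analysis accounts for it

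*Combined protocol and SAP*

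**What the plan says.** Section 5 calls the trial a "prospective, single-surgeon, non-randomized controlled study conducted at a single medical center". Section 6 (Grouping) sets the mechanism and its timing: "After surgery, enrolled patients will be divided into two groups based on personal willingness". The flow diagram in Section 6 gives the same order, with consent and baseline polysomnography (PSG) first, then "Undergo Surgery (UPPP)] -> [Post-op Group Allocation". On treatment, Section 6 states: "Group A patients will begin a 12-week MFT program starting at the third postoperative week".

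The measurement schedule in Section 6 is: "All participants will undergo overnight polysomnography (PSG) at the sleep center at baseline (pre-surgery), and at 3 and 12 months post-surgery". The data named are these: "Objective data on AHI, LSaO₂, and snore index will be collected". The only other postoperative record is in Section 7: "During all follow-up visits, researchers will actively monitor and record any adverse events related to either the surgery or the MFT". The dates of those visits are not given.

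Section 8 compares continuous variables by paired or unpaired t-tests and categorical outcomes by chi-square. It has no covariates, matching, weighting or sensitivity analysis. Section 13 lists sample size, length of follow-up and self-reported adherence as anticipated problems. Self-selection is not among them.

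**The concern.** Declaring a design non-randomised warns the reader that the groups may differ at baseline. The timing here adds a second problem. A choice recorded before surgery can depend only on what is known before surgery. A choice made after surgery can also depend on how the operation has gone so far, and the primary outcome is AHI after that same operation.

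If patients who recover well are more willing to exercise, part of a good surgical result is credited to MFT. If patients who still have symptoms are more willing, a real benefit of MFT is partly hidden. Section 10 expects strong evidence that could influence guidelines, so the group difference will be read as an effect of MFT.

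**Working it through.** **No figure to reproduce.** The documents give no sample size, power, effect size, SD of AHI or allocation ratio. The calculation below is an illustration, and every input is an assumption.

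**Inputs.**
- Outcome standardised to SD 1; no true MFT effect; even split between groups.
- Early recovery U, standard normal, with correlation ρ = 0.2, 0.3 or 0.5 with the outcome.
- Odds of choosing MFT multiplied by 1.5 or 2 per SD of U, so g = ln 1.5 = 0.405 or ln 2 = 0.693.
- Total N of 60 or 100; two-sided 5% t-test as in Section 8 (sidedness is not stated there).

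**Step 1: difference in recovery between the groups.** With p = 1/(1 + exp(−gU)), the difference in mean U is D = 4g × E[p(1 − p)].
- Odds ratio 1.5: 4 × 0.405 × 0.2405 = 0.390.
- Odds ratio 2: 4 × 0.693 × 0.2254 = 0.625.

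**Step 2: bias and error rate.** Bias = ρ × D. The standard error of the group difference is about 2/√N, so δ = bias × √N / 2, and the error rate is Φ(−1.96 + δ) + Φ(−1.96 − δ).

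Worked example (odds ratio 2, ρ = 0.3, N = 60): bias = 0.3 × 0.625 = 0.188; δ = 0.188 × 7.746 / 2 = 0.73; error = Φ(−1.23) + Φ(−2.69) ≈ 11%.

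| Odds ratio per SD | ρ | Bias (SD) | Error, N = 60 | Error, N = 100 |
|---|---|---|---|---|
| 1.5 | 0.2 | 0.08 | 6.1% | 6.8% |
| 1.5 | 0.3 | 0.12 | 7.4% | 9.0% |
| 2 | 0.2 | 0.13 | 7.7% | 9.6% |
| 2 | 0.3 | 0.19 | 11.2% | 15.5% |
| 2 | 0.5 | 0.31 | 22.8% | 34.6% |

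A simulation with 3,000 runs per setting gave 11.0% for the worked example and 5.1% for the weakest setting at N = 60. Weak selection is therefore barely distinguishable from the nominal rate. With ρ = 0 the error stayed at about 5%.

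**Step 3: what adjustment can do.** In the same simulation a baseline covariate correlated 0.5 with the outcome and was unrelated to early recovery. At N = 60, ρ = 0.3 and odds ratio 2, the error was 11.0% for the t-test, 13.8% after baseline adjustment, and 5.0% after adjustment for both baseline and early recovery. The bias was 0.19 SD with or without baseline adjustment. The error rises slightly because residual variance falls while the bias stays. If baseline predicted part of early recovery, adjusting for it would remove that part only.

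**Step 4: grouping by a pre-surgery choice.** With the same inputs the t-test's error returns to about 5%, provided that the earlier choice is itself unrelated to outcome. The price is dilution. Suppose each patient has a stable preference and recovery shifts it by g per SD. The share who switch is s = E[1/(1 + exp(−g|U|)) − 0.5], which is 0.079 at odds ratio 1.5 and 0.129 at odds ratio 2. With switching equal in both directions, the share of a true effect kept is 1 − 2s.
- Odds ratio 1.5: 1 − 2 × 0.079 = 0.84; patients needed for equal power, 1/0.84² ≈ 1.4 times.
- Odds ratio 2: 1 − 2 × 0.129 = 0.74; patients needed, 1/0.74² ≈ 1.8 times.

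**The case against.** The strongest reply has four parts.

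*The design is openly non-randomised.* This is true, and Section 5 says so. The label does not tell a reader that the choice may follow the early surgical result, and it corrects nothing.

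*The influence of recovery is conjecture.* This stands as a limit on the claim. A reader might infer that recovery does drive the choice, that patients already know their result at week 3 when they choose, or that the bias favours MFT. The documents support none of these. They give week 3 as the start of MFT, not as the moment of choice. A patient may have decided before surgery, and either direction of bias is plausible.

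*Postoperative events are recorded.* Section 7 has adverse events recorded at follow-up visits and names pain and bleeding as possible complications, so it would be too strong to say that nothing about recovery is captured. But the timing of those visits relative to the choice is not stated, and no analysis uses the records.

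*An earlier choice is no cure.* Much of this stands. Dilution of 16–26% is not slight for a study that already calls its sample modest. The comparison then concerns choosing MFT before surgery, whereas Section 4 asks about adding the programme. Motivation and general health behaviour also operate before surgery and are not listed among the data. What survives is narrower: asking before surgery closes the path through the operation's early result, which later asking leaves open.

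**Conclusion.** The concern holds in limited form. The plan lets early postoperative recovery influence group membership, schedules no measure of it before grouping, and uses unadjusted tests. Under the assumed inputs the bias is about 0.08–0.31 SD. The t-test's error rate is about 6–9% at an odds ratio of 1.5 and correlations of 0.2–0.3, about 8% to just over 15% at an odds ratio of 2 and the same correlations, and about 22–35% at a correlation of 0.5. These figures rest on assumed N, correlations and selection strength, and an even split.

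Two stronger readings should be avoided. The bias cannot be given in events per hour, because the documents contain no AHI distribution or SD from which to convert it. Nor can it be said that baseline data are useless: they would remove whatever part of recovery they predict, and the plan does not use even that.

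**What to change.** 1. **Section 6 and the flow diagram:** record willingness for MFT at informed consent, before surgery. Define Groups A and B for the primary comparison by that answer. Patients remain free to change their minds.
2. **Section 8:** adjust the primary comparison for baseline AHI. Without this, self-selection that exists before surgery stays uncorrected.
3. **Just before MFT would start:** record the final choice, the reason for any switch, and a brief symptom and recovery rating. Report the number of switches in each direction. As a sensitivity analysis, give the comparison by actual group, adjusted for baseline AHI and that rating.
4. **Sections 10 and 13:** add self-selection to the anticipated problems, state that the primary result describes choosing MFT before surgery rather than receiving it, and soften the causal wording.

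The cost is a few questions at existing contacts, plus the dilution shown above: about 8–13% switching, with about 74–84% of a true effect kept, if recovery shifts the choice odds by 1.5–2 per SD. Unmeasured pre-surgery motivation remains, and only randomisation would remove it.

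Section 5 describes the project in the past tense. If grouping is already complete, items 1 and 3 are no longer possible. What remains is baseline adjustment, a sensitivity analysis for unmeasured confounding, and item 4 without its statement on pre-surgery choice.
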